5 PROCEDURES

5.1 Study procedures. Using lay language, provide a complete description of the study procedures, including the sequence, intervention or manipulation (if any), drug dosing information (if any), blood volumes and frequency of draws (if any), use of records, time required, and setting/location. If it is available: Upload a study flow sheet or table to **Zipline**.

For studies comparing standards of care: It is important to accurately identify the research procedures. See UW IRB [POLICY Risks of Harm from Standard Care](#) and the draft guidance from the federal Office of Human Research Protections, ["Guidance on Disclosing Reasonably Foreseeable Risks in Research Evaluating Standards of Care"](#); October 20, 2014.

Information about pediatric blood volume and frequency of draws that would qualify for expedited review can be found in this [reference table](#) on the Seattle Children's IRB website.

Research activities will be conducted by UW and [REDACTED] staff and begin the first week of class: for the waitlist group – the group starting in spring, they will only take the baseline assessment in the Fall and begin the intervention steps as described below beginning in the spring. Thus they receive one more assessment than students in the immediate intervention group (fall). UW staff will be on hand to answer any questions at each assessment time point. Please note the follow-up assessment are about 10 minutes shorter as we will not be any lifetime behaviors questions

Week 1. Take a 30-40 minute online baseline assessment.

UW and [REDACTED] staff will set up laptops or students will have their own laptop. Students will be emailed a link, they will sign onto their laptops and link into the survey. The student

will enter their response directly into the questionnaire. Students will be given a Native designed t-shirt and water bottle.

Weeks 1-3. Meet with a mentor who will help students set goals to improve their health goals around sexual health and/or reduce or avoid alcohol, tobacco, or other substance use. They may meet with the mentor one more time within this time period (for a total of two meetings). The masters-level mentors are provided by the [REDACTED] and trained by a certified motivational interviewer trainer hired by UW.

Week 1 – 8 (month 1-2). As part of their health class, attend 16 health sessions related to healthy behaviors and developing behavioral skills for health promotion. Sessions will be led by [REDACTED] staff. The study session curriculum will emphasize youth as leaders, storytellers, and environmental stewards and highlight the importance of connecting to their own tribal traditions.

Week 9- 16 (month 3-4). **Optional** additional activity. Participate in once a month activity (booster sessions).

The activities will help build youth leadership skills and include drum making, and storytelling vest making that incorporate their own cultural symbols, and up to two outdoor activity field trips. The field trips are to a places of cultural significance near the school and involve a 30-45 minute hike. Activities are between 1-2 hours and delivered by the [REDACTED] staff after school or on weekends.

Week 9 (Month 3) take the online post intervention assessment via a link sent to their email address by the UW staff

Week 16 (month 4) **Optional** additional activity. Meet with their mentor for a booster MI session to revise their vows for health and community leadership.

Week 9 -24 (month 3 - 6). **Optional** additional activity. Attend a digital storytelling training and up to three monthly planning sessions to prepare for digital storytelling leadership premiere night. Training and planning sessions are 1-2 hours long and held after school. Students will be asked to create a digital story about a health promotion activity of their choice for their community. Some examples may be an increase in cultural activities through participating in traditional games, an increase in promoting healthy lifestyle by planting a traditional garden or a medicine garden base on their own tribal plants. These activities are delivered by the UW and [REDACTED] staff.

Week 24 (Month 6) take the online follow-up assessment via a link sent to their email address by the UW staff

Week 25 (Month 6): **Optional** additional activity. Attend a leadership premiere night, present their digital stories and/or share a story that they have learned about health promotion and celebrate their health leadership journey.

Help prepare the leadership night traditional feast and giveaway that will honor their community culture and values.

Month 12: Take the online follow-up assessment via a link sent to their email address by the UW staff

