Journey of Transformation Curriculum for Native American Adolescents (JOT)

NCT05274217

[name]

Statistical Analysis Plan

IRB Approved 03-16-2021

Statistical Design and Power

This study will evaluate the following primary outcomes: (1) alcohol, tobacco, and other drugs (ATOD; intentions to use, overall use, susceptibility, refusal self-efficacy) and (2) sexual and reproductive health (sexual activity, sexual self-efficacy, safer sex intentions). An intent-to-treat approach will be used to estimate the magnitude and statistical significance of intervention effects at immediate post-intervention. Each outcome will be evaluated in a separate generalized linear mixed model to evaluate the effect of CHJOT curriculum on intervention outcomes. Continuous outcomes will be modeled using a Gaussian link function for normally distributed data and binary outcomes using a logit link for Bernoulli-distributed data. The following equation represents the basic model for the outcomes: $Outcome_{tij} = b_0 + b_1 Intervention_i + b_2 Time + b_3 (Intervention_{ij} \times Time_{tij}) + u_{0i} + r_{0ij} + e_{tij}$, where t indexes assessment, i indexes individual, and j indexes classroom. The last three terms on the right side of the model equation represent the variability between classrooms (u_{0i}), between individuals within classroom (r_{0ij}), and residual error (e_{tij}), respectively. The statistical test of the CHJOT curriculum will be the Intervention by Time interaction, which will evaluate whether recipients of the intervention curriculum improved more or decreased less from pre- to 2-month post-intervention compared with waitlist control.

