To estimate the necessary sample size for our Longitudinal Mediation Model. We assume 80% power to detect a small intervention effect of $d = 0.22$ (standardized mean effect) of CJT (immediate intervention) vs. Waitlist control in pre-intervention to 3 month post-intervention outcome change. We base our power analysis on a repeated measures ANOVA design evaluating the Intervention by Time interaction in the primary outcome analysis, assuming a Type I error rate of 5%. Assuming a moderate temporal stability ($r = .25$) of the outcome measures, which is reasonable given the short interval between assessments, post-baseline data from 255 participants will be necessary to detect an intervention effect equivalent to a Cohen's d as low as 0.20, which would accommodate a 10% reduction in the observed intervention effect due to potential early exposure of control participants to the intervention (i.e., contamination effects). We anticipate a modest attrition rate of 15%, as the intervention will be offered in a required class in a boarding school indicating an analytic sample of 216 participants. Thus, our planned recruitment of 255 participants will provide a sufficient sample to detect targeted intervention effect, after accounting for attrition.

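### As protocol 5.1 is written, no waitlist survey coincides with the immediate arm's Fall Week 9 post-test, so the SAP's primary contrast has no concurrent untreated comparison

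*Protocol*

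**What the plan says.** **Schedule (protocol 5.1).** Of the waitlist group it says: "they will only take the baseline assessment in the Fall and begin the intervention steps as described below beginning in the spring". It adds: "Thus they receive one more assessment than students in the immediate intervention group (fall". The first listed step is a Week 1 baseline survey. The post-test is: "Week 9 (Month 3) take the online post intervention assessment via a link sent to their email address by the UW staff". Further surveys follow at Week 24 and Month 12.

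**Primary analysis (SAP, Statistical Design and Power).** The aim is to estimate the "magnitude and statistical significance of intervention effects at immediate post-intervention". The test is the Intervention by Time interaction, that is, whether recipients "improved more or decreased less from pre- to 2-month post-intervention compared with waitlist control". On the time index the SAP says only "where t indexes assessment, i indexes individual, and j indexes classroom".

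**Power paragraph (SAP).** "We base our power analysis on a repeated measures ANOVA design evaluating the Intervention by Time interaction in the primary outcome analysis". Here the interval ends three months post-intervention. The effect size is reduced by 10% "due to potential early exposure of control participants to the intervention (i.e., contamination effects", so controls are otherwise taken to be untreated at the post-test.

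**The concern.** A waitlist design identifies the effect by observing, at the moment the first group finishes, what happens to students who have not yet started. That needs an untreated control value at the same time as the post-test. Protocol 5.1 does not appear to collect one, and the SAP does not name the survey that would stand in for it.

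A control value not collected at Fall Week 9 cannot be recovered in analysis. Someone would have to choose the control's second time point, and the coding of Time, after the data are in, for every primary outcome. Randomisation does not protect the contrast, because the arms would then differ in when they are measured as well as in treatment.

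**Working it through.** **1. Count the surveys, reproducing the protocol's own figure.** Inputs are the survey steps in protocol 5.1. F and S denote Fall and Spring of a cohort.

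| Arm | Surveys as 5.1 reads | Number |
|---|---|---|
| Immediate | F Week 1, F Week 9, F Week 24, Month 12 | 4 |
| Waitlist | F Week 1, then S Week 1, S Week 9, S Week 24, S Month 12 | 5 |

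5 − 4 = 1, which matches the stated one extra assessment. The only occasion the text fixes as common to both arms is F Week 1. Adding a waitlist F Week 9 survey to this list would make the difference 6 − 4 = 2, against the text. Replacing S Week 1 by F Week 9 would keep the difference at 1 but contradict the statement that only the baseline is taken in the Fall.

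**2. Write out the contrast.** Let δ be the curriculum effect at its end. Let P(x) be the change an untreated student would show from F Week 1 to occasion x, equal in expectation across arms by randomisation.

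- Immediate arm, F Week 1 to F Week 9: δ + P(F9).
- Waitlist arm, F Week 1 to S Week 1: P(S1).
- Pre/post interaction: δ + P(F9) − P(S1).

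P(F9) is observed untreated in neither arm, so δ is separable from calendar time only by assuming a shape for P. A rank check agrees. With arm and calendar-period terms for these four arm-by-occasion cells, the design rank is 4 without the treatment column and 4 with it. With a waitlist F Week 9 survey in place of S Week 1, the rank rises from 3 to 4 and the interaction is δ + P(F9) − P(F9) = δ.

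**3. Try the other substitute.** The waitlist's change from S Week 1 to S Week 9 is δ + P(S9) − P(S1), assuming equal effects in both arms. The interaction is then P(F9) − [P(S9) − P(S1)]. The effect cancels, because both groups have been treated.

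**4. Distance in time.** If Spring Week 1 falls in calendar week s counted from Fall Week 1, it comes s − 9 weeks after the immediate post-test. The documents give no term dates. Assuming s = 14 to 26, the gap is 14 − 9 = 5 to 26 − 9 = 17 weeks. Relative to the immediate arm's Week 24 survey, Spring Week 1 would lie between 10 weeks before (s = 14) and 2 weeks after (s = 26), and would coincide at s = 24.

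**5. Coding of Time.** The repeated measures ANOVA behind the power calculation suggests two levels, pre and post, which is the case in step 2. If Time were instead elapsed time, a linear drift common to both arms would be absorbed. A non-linear or term-specific change would not be, and the comparison would still not be concurrent.

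**The case against.** **The evidence is one lay sentence.** Protocol 5.1 is an IRB form answer in plain language. Its *only* could mean that the waitlist group gets no mentoring or sessions in the Fall, rather than no second survey. The form also invites a separate flow sheet, which is not among the documents. This limits confidence. It does not supply a survey: on either sense of the word, no text schedules a waitlist survey at Fall Week 9, and the SAP definition is missing either way.

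**The count is not proof.** A reader might infer that the extra assessment settles the matter. It does not. Five waitlist surveys could also be Fall Weeks 1 and 9 plus three from spring. If that was intended, the sentence in 5.1 is wrong and needs correcting.

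**An untreated comparison does exist.** A reader might infer that the trial has no untreated control data after baseline. That goes too far. Spring Week 1 is untreated, and if spring starts near week 24 it is roughly concurrent with the immediate arm's Week 24 survey. That is not the SAP's primary time point, so it does not rescue the primary contrast.

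**A size for the bias is tempting.** One could assume a monthly drift, derive an inflated type I error and set the shift against d = 0.20. The documents do not support this: drift and term dates would all be assumed, and the scales may not match. With 216 analysed, 108 per arm and r = .25, the standard error of a difference in change is √(2 × 0.75) × √(2/108) = 0.167 SD. A true difference of 0.20 SD would then have about 22% power, not 80%. Under the usual repeated measures convention f = d/2, noncentrality at d = 0.20 is 0.10² × 216 × 2 / 0.75 = 5.76, with square root 2.4. That corresponds to 2.4 × 0.167 = 0.40 SD in change.

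**Payment.** A reader might also infer that the payment schedule in protocol 4.4 cannot fit five waitlist surveys. Two unpaid baselines plus three paid follow-ups do fit. Only the ordinal labels (second, third, final) do not.

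**Conclusion.** The concern holds on the schedule as written. Followed literally, protocol 5.1 leaves the SAP's primary contrast without a concurrent untreated value at Fall Week 9. Of the possible stand-ins, Spring Week 1 is later and in another term, and Spring Week 9 is already treated. Under pre/post Time the estimate is δ + P(F9) − P(S1). The bias term is zero if untreated students do not change between the two occasions, and its size and direction cannot be determined from the documents.

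The conclusion assumes that *only* is meant literally or that no Fall Week 9 waitlist survey is scheduled elsewhere. Confidence is therefore medium. It should still be settled before any further cohort starts, because the missing measurement cannot be replaced later and the correction is small.

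A lesser point: the SAP's three descriptions of the post-test (immediate, two months, three months) probably all mean the Week 9 (Month 3) survey. One label should be used.

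**What to change.** **Protocol 5.1.** Give the waitlist arm the existing online follow-up survey at Fall Week 9, on the same days as the immediate arm.

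- *Option A, move the Spring Week 1 survey there.* This keeps 5 versus 4 surveys. The downside is that the spring re-baseline is lost: the waitlist's last untreated measure would be 5 to 17 weeks old when it starts, under the assumed start in week 14 to 26. Suggested text: *In the Fall, waitlist students complete the baseline survey and, on the same days as the immediate group, the Week 9 survey. They start the curriculum in spring without a second baseline.*
- *Option B, add it and keep Spring Week 1.* This gives 6 versus 4. It adds one sensitive survey of 20–30 minutes (30–40 less about 10) for minors. It is needed only if the waitlist's own before-and-after change is to be analysed, as the stepped-wedge label in protocol 1.6 may imply.

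Under either option both arms have had the same two surveys at the primary contrast.

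**SAP.** Suggested text: *The primary contrast is change from Fall Week 1 to Fall Week 9 (Month 3) in both arms, before the waitlist arm begins the curriculum; Time = 0 at Week 1 and 1 at Week 9.* Use that label throughout.

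**Protocol 4.4.** State which waitlist surveys are paid.

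**If a flow sheet already schedules a waitlist Fall Week 9 survey**, correct 5.1 to match and add the SAP definition.

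**Cost.** An IRB modification and a few sentences. If each waitlist Fall Week 9 survey brings an extra $20 payment (the first follow-up rate in 4.4) and arms are equal, the cost is 20 × 127.5 = $2,550 for 255 recruits, or 20 × 225 = $4,500 for the 450 maximum in protocol 2.8. Option A costs nothing extra if Spring Week 1 was already to be paid, which the documents do not say. Protocol 4.4 reports the project discontinued for the year, so the change can precede any later cohort's Fall term.

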7 ASSENT OF CHILDREN (MINORS)

Go to [Section 8](#) if your research does not involve children (minors).

7.1 Assent of children (minors). Though children do not have the legal capacity to “consent” to participate in research, they should be involved in the process if they are able to “assent” by having a study explained to them and/or by reading a simple form about the study, and then giving their verbal choice about whether they want to participate. They may also provide a written assent if they are older. See [WORKSHEET Children](#) for circumstances in which a child’s assent may be unnecessary or inappropriate.

a. Will assent be obtained for:

All research procedures and child groups

→ Go to [question 7.2.](#)

None of the research procedures and child groups

→ Use the table below to provide justification, then skip to [question 7.6](#)

Some of your research procedures and child groups

→ Use the table below to identify the procedures for which assent will not be obtained.

Be sure to consider all research procedures and plans, including screening, future contact, and sharing/banking of data and specimens for future work.

Children Group ¹	Describe the procedures or data/specimen collection (if any) for which assent will NOT be obtained	Reason why assent will not be obtained

Table footnotes

1. If the answer is the same for all children groups or all procedures, collapse your answer across the groups and/or procedures.

7.2 Assent process. Describe how assent will be obtained, for each child group. If the research involves children of different ages, answer separately for each group. If the children are non-English speakers, include a description of how their comprehension of the information will be evaluated.

For students whose parent/guardian indicated they have permission to take the class, they will be invited to attend a research orientation meeting during their onsite school orientation. Students arrive to the school two weeks before classes start to move into their dorms, settle in, learn about class topics for the year and school activities. A research orientation session will occur during the first week of their 2-week pre-school orientation period.

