At the orientation meeting, a study package will be handed to each youth. The package will include Native items such as sage or lavender, a writing pad and pen and pencil with a Native design and study phone number, two copies of the assent form (one for them to sign and the other to keep as their copy), and the study flyer. UW and [REDACTED] staff will inform the students about the research project, highlighting that it is

completely voluntary and then review the assent form and ask for questions. At the end of the meeting, students will be instructed to write their names on the assent form and indicate if they are interested in participating in the project (Yes/No) or would like more information. Students who are interested in participating will also be asked to fill out a contact information sheet, which asks for their name(s), birth date, preferred pronouns, email address, phone number, and space to provide any additional contact information (ex., social media). If they would like more information, they will be asked to provide contact information (similar to that of those who have assented) and a UW staff person will contact them. They will be informed that they may also reach out to the UW or [REDACTED] staff at any time before the first day of class (within the two weeks) if they have any additional questions about participation.

Students will hand in one signed copy of the assent form when they exit the room.

UW or [REDACTED] staff will then follow-up with students that indicated they are interested in participating and welcome them to the program and asked if they have any additional questions. They will also follow-up with students who request additional information.

For students that have indicated they are interested, they will be randomly assigned to a class offering the intervention sessions. Some classes will start the intervention curriculum in the Fall, others in the Spring. Students that indicated they are not interested they will be assigned to a class that is not participating in the intervention curriculum. This is easily done as there are multiple classes for each grade.

Students may choose to drop out of the research program by notifying research staff by email and reassignment to a health class will be provided. As standard practice, students periodically change class assignments so this would not seem out of the norm.

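### The baseline survey is set for Week 1 of class, apparently after open assignment to arm, and nothing requires it to precede disclosure of arm or first intervention contact

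*Protocol*

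**What the plan says.** Protocol 7.2 (Assent process) dates the assent meeting: "A research orientation session will occur during the first week of their 2-week pre-school orientation period". Of students who say they are interested it then states that "they will be randomly assigned to a class offering the intervention sessions", and adds: "Some classes will start the intervention curriculum in the Fall, others in the Spring". The class therefore determines the arm. The sentence on random assignment carries no date of its own.

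Protocol 5.1 (Study procedures) says that research activities "begin the first week of class: for the waitlist group", and of the waitlist that "they will only take the baseline assessment in the Fall". The timetable then runs:

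- Survey: "Week 1. Take a 30-40 minute online baseline assessment".
- Mentoring: "Weeks 1-3. Meet with a mentor who will help students set goals". The goals concern sexual health and substance use.
- Curriculum, Weeks 1 to 8: "As part of their health class, attend 16 health sessions related to healthy behaviors".

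Protocol 10.7 (Un-blinding) describes no blinding. The SAP (Statistical Design and Power) tests the Intervention by Time interaction, b3, from the pre value to the post-intervention value against the waitlist.

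**The concern.** A baseline serves as the reference for change because it cannot have been influenced by the allocation. That is assured when it is collected before allocation, or at least before anyone can react to it. Here the survey is open self-report, it appears to follow assignment to a class that reveals the arm, and it shares its week with the first intervention activities. A student who knows that the programme starts now may answer questions on intentions, susceptibility or refusal efficacy differently from one who knows that it starts in spring. A student who has already met a mentor may do so for a different reason.

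If the two arms' baselines diverge for such reasons, the difference enters the primary contrast. The analysis cannot separate it from chance imbalance.

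**Working it through.** **1. The plan's own figure.** The documents give no figure on survey timing. The only figure for the pre-post test is the SAP's 255 participants (80% power, r = 0.25, alpha 5%, d = 0.22 reduced to 0.20). The closest reading is a repeated-measures ANOVA interaction with two groups and two times: f = d/2, noncentrality = f² × N × 2/(1 − r), F on 1 and N − 2 degrees of freedom. I assume 1:1 allocation and a two-sided test.

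- d = 0.20, f = 0.10: N = 298 (234 one-sided). Power at 255 is 73.8%.
- d = 0.22, f = 0.11: N = 246. Power is 81.5% at 255 and 74.8% at 216.
- Attrition: 255 × 0.85 = 216.75, which agrees with the SAP's 216.

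The 255 does not reproduce exactly. The timing point does not depend on it.

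**2. Order of events.**

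| Event | Stated timing | Source |
|---|---|---|
| Assent meeting | First week of the two-week orientation | Protocol 7.2 |
| Random assignment to class | Undated; follows assent in the text | Protocol 7.2 |
| Students told their class | Not stated | – |
| Baseline survey | Week 1; waitlist also in the Fall | Protocol 5.1 |
| Mentor meetings | Weeks 1-3 | Protocol 5.1 |
| 16 sessions | Weeks 1-8 | Protocol 5.1 |

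The waitlist is already a named group when it takes its fall baseline, so assignment has apparently happened by then. The survey goes out by emailed link and no completion cut-off is stated.

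**3. How a shift reaches b3.** The SAP model gives the arms separate baseline means (b1), so for a continuous outcome b3 is a difference in changes. Let δ be the intervention-minus-waitlist shift at baseline caused by assignment, and ε the same kind of reporting shift at follow-up.

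- Bias in b3 = ε − δ.
- Shift confined to baseline (ε = 0): bias = −δ, the whole shift with its sign reversed.
- Equal reporting shift at both times (ε = δ): bias = 0.
- Baseline entered as a covariate (ANCOVA), shift confined to baseline: bias = −slope × δ. With equal variances the slope is r = 0.25, so a quarter passes through.

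**4. Illustrative sizes, all on assumptions.**

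- Sessions in the baseline week: 16/8 = 2 per week, and 2/16 = 12.5%. This is an upper bound that assumes even spacing and a survey taken after both sessions. If the survey comes first, the figure is 0 of 16.
- Shift of 0.05 SD: 0.05/0.20 = 25% of the target under the SAP's test. With baseline as a covariate, 0.25 × 0.05 = 0.0125 SD, and 0.0125/0.20 = 6.25%. These shares take d as the between-arm difference in change in outcome SDs. Under the f = d/2 convention that difference is 4f = 2d = 0.40 SD, and the shares halve.
- Dilution: if the intervention arm's baseline already carries a share q of the effect, the detectable effect is d(1 − q). With d = 0.22:

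| q (assumed) | d(1 − q) | Power, N = 255 | Power, N = 216 |
|---|---|---|---|
| 0 | 0.220 | 81.5% | 74.8% |
| 5% | 0.209 | 77.5% | 70.4% |
| 10% | 0.198 | 73.0% | 65.7% |
| 20% | 0.176 | 62.8% | 55.7% |

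The SAP's 10% allowance concerns control participants exposed early, which is a different mechanism.

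**The case against.** The strongest reply is that the documents lean towards survey first. The form behind 5.1 asks for the sequence, and baseline is the first item. The same section separates the baseline from the intervention steps that follow, and the SAP calls the comparison value pre-intervention. Protocol 4.4 describes a year in which students finished the first survey and never received the intervention. This stands as far as it goes. It makes prior exposure to content less likely, but listing order is not a completion rule, and survey-first within Week 1 does nothing about knowledge of arm.

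A reader might infer that students are known to have learned their arm before the survey. The documents do not say so. The only hint of earlier notice is the reminder to the spring wave in Protocol 7.6. It goes out the week before Spring, after the fall baseline, and cannot show what students knew in Week 1.

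Two statistical points also stand. First, a reporting shift that persists to follow-up cancels in b3 under the present schedule, and moving only the baseline ahead of disclosure would expose it. That cancellation needs equal shifts at both times, which the data cannot confirm. A baseline free of assignment leaves only the usual limitation of open self-report at follow-up. Second, covariate adjustment would remove most of a shift confined to baseline at r = 0.25, so such a shift is not beyond repair. The SAP does not plan that adjustment.

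Finally, items that look back 30 days or 12 months (Protocol 5.4) can hardly change in truth within days, although the way students report them can.

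**Conclusion.** The concern holds as an avoidable bias risk, not a demonstrated bias. On the text, an unblinded self-report baseline is set for Week 1 of class, apparently after assignment to a class that reveals the arm, in the week when mentoring and sessions can begin. No safeguard places it before disclosure or first contact. Because the primary test is change from that value, a shift confined to one arm's baseline would bias b3.

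The direction is unknown: a shift towards the intervention effect dilutes b3, and the opposite shift inflates it. The risk is most plausible for intentions, susceptibility and efficacy scales, and weaker for recalled behaviour.

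The documents support no size. The 12.5%, the 0.05 SD and the shares q are assumptions that show sensitivity only. A reader might conclude that a quarter of the target effect is at stake, or that any shift passes in full into the estimate. The first rests on an assumed shift and one reading of d. The second is true only for a shift confined to baseline and analysed as change.

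**What to change.** Give the baseline survey to both arms during the two-week pre-class orientation, after assent and before class assignments are released. State that order in Protocol 5.1 and 7.2, and state when students are told their class.

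If the school cannot accommodate this, require in both arms that the survey be completed before any session or mentor contact. Record each student's completion date alongside the dates of first session and first mentor meeting. This fallback deals with exposure to content but not with knowledge of arm.

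The cost is 30-40 minutes in a busier orientation, a change to the IRB wording, and agreement with whoever releases class lists, whom the documents do not name. Study staff already meet students in orientation for assent, but the documents do not show staffing for a supervised survey then. Students may raise questions about participation until the first day of class, so late deciders need a route to complete the survey before they are told their class. The sample size is unchanged. Recruitment is in annual waves (Protocol 1.6), so any later cohort could adopt the change.
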